
Name of Investigational Product: Allogeneic Micronized Dehydrated Human Amnion/Chorion Membrane (Micronized dHACM), a.k.a. AmnioFix Injectable
 
Study Design: A Phase 2B, Prospective, Double-Blinded, Randomized Controlled Trial of the Micronized dHACM Injection as Compared to Saline Placebo Injection in the Treatment of Osteoarthritis of the Knee
 
Indication: Knee osteoarthritis (OA)
 
Objective: To determine the safety and effectiveness of micronized dHACM as compared to the 0.9% Sodium Chloride Injection, USP placebo control for the treatment of knee osteoarthritis
 
Sample Size: Approximately 466 subjects will be enrolled in this study. Subjects to be randomized 1:1 in treatment arms.
 
Study Plan: The estimated enrollment period is 26 months. Each subject will receive 1 injection and be evaluated for efficacy and safety during a 12-month observation period. A second injection (open-label access to micronized dHACM) will be offered to all subjects at the 180-day, 270-day, and 365-day time points, see open-label access section below; it may only be used once. The study is expected to be completed within 44 months, inclusive of enrollment and follow-up for all subjects.
 
Procedures and Assessments:
 
 • Treatment (approx. 1 day): Screening, pre-procedure evaluation, injection procedure, baseline evaluation. • Clinical Follow-up (365-545 days): Routine follow-up with physical examination; pain, function, and quality of life measurements: Visual Analog Scale (VAS) for Pain, VAS for Satisfaction, Western Ontario and McMaster Universities (WOMAC) osteoarthritis index, and Knee injury and Osteoarthritis Outcome Score (KOOS) will be evaluated at baseline, 30 days, 60 days, 90 days, 180 days, 270 days and 365 days after the initial treatment, and at time of open-label access and 30 days, 60 days, 90 days, and 180 days following the second injection should the subject elect to receive the open-label access treatment. Subject pain diaries will be completed at predefined intervals. • Safety Follow-up (365-545 days): Adverse Events (AEs), Serious Adverse Events (SAEs), and Unanticipated Adverse Events will be evaluated at 30 days, 60 days, 90 days, 180 days, 270 days and 365 days after the initial treatment, and at time of open-label access and 30 days, 60 days, 90 days, and 180 days following the second injection should the subject elect to receive the open-label access treatment. 
Primary Efficacy Endpoints (VAS for Pain and Total WOMAC): The co-primary efficacy endpoints are:
 
 • The change in VAS score for pain between baseline and Day 90 • The change in WOMAC osteoarthritis index total score (Total WOMAC score) between baseline and Day 90 
Primary Safety Endpoint: The primary safety endpoint is the proportion of product-related Adverse Events (AEs), Serious Adverse Events (SAEs), and unanticipated adverse events throughout the study.
 
Secondary Endpoints: The secondary efficacy endpoints for this study are:
 
 • Change in VAS score for pain between baseline and 180 days • Change in Total WOMAC score between baseline and 180 days

Exploratory Endpoint:

For the cohort of subjects in the main phase of the study, i.e. who did not receive or have not yet received an open-label injection, the following exploratory endpoints will be assessed:

- Change in VAS score for pain between baseline and i-day (with i=30, 60, 270, and 365 days)
- Change in Total WOMAC score between baseline and i-day (with i=30, 60, 270, and 365 days)
- Change in pain, stiffness, and physical function WOMAC subscale scores between baseline and i-day (with i=30, 60, 90, 180, 270, and 365 days)
- Change in VAS score for satisfaction between baseline and i-day (with i=30, 60, 90, 180, 270, and 365 days)
- Change in KOOS scores between baseline and i-day (with i=30, 60, 90, 180, 270, and 365 days)
- Patient pain diary endpoints will be collected and summarized across applicable time points

For the cohort of subjects in the extension phase, i.e. who received the open-label injection and are within the period after the open-label injection, the following endpoints will be collected and summarized across applicable time points: VAS score for pain, Total WOMAC, WOMAC subscales for pain, stiffness and physical function, VAS score for satisfaction, KOOS, and pain diary entries.

Inclusion Criteria

All subjects enrolled must meet all the following criteria:

1. Age \geq 21 and \leq 80 years
2. Subject has a diagnosis of osteoarthritis (OA) defined as Grade 1 to 3 on the Kellgren Lawrence grading scale
3. Subject is willing and able provide informed consent and participate in all procedures and follow-up evaluations necessary to complete the study
4. Subject must have a VAS pain scale greater than 45

Exclusion Criteria

Any potential subjects meeting any of the following criteria will be excluded from enrollment and subsequent randomization.

1. Subject has a diagnosis of osteoarthritis (OA) defined as Grade 4 on the Kellgren Lawrence grading scale
2. BMI greater than 40 kg/m²
3. Subject has active infection at the injection site
4. Symptomatic OA of the contralateral knee or of either hip that is not responsive to acetaminophen (Tylenol®) and requires other therapy.
5. Subject has rheumatoid arthritis, psoriatic arthritis, or have been diagnosed with any other disorders that is the primary source of their knee pain, including but not limited to: osteonecrosis, radiculopathy, bursitis, tendinitis, tumor, cancer
6. Subject has documented history of gout or pseudo-gout
7. Subject has autoimmune disease or a known history of having Acquired Immunodeficiency Syndromes (AIDS) or HIV
8. Subject has received any of the following to the target knee:
 - a. Intra-articular hyaluronic acid (HA) injection within 12 weeks prior to screening
 - b. Steroid or platelet rich plasma (PRP) injection within 12 weeks prior to screening
 - c. Has had or is planning to have major surgery or arthroscopy in the target knee within 26 weeks of treatment
 - d. History of a total knee arthroplasty
9. Subject has used an investigational drug, device or biologic within 12 weeks prior to treatment
10. Subject has a history of immunosuppressive or chemotherapy in the last 5 years
11. Subject has had prior radiation at the site
12. Subject is currently taking anticoagulant therapy (excluding Plavix or Aspirin)
13. Subject is pregnant or plans to become pregnant within 365 days of treatment
14. Subject has any significant medical condition that, in the opinion of the Investigator, would interfere with protocol evaluation and participation
15. Subject is a worker's compensation patient
16. Subject is a prisoner

Open-Label Access:

All study subjects will be eligible to receive one injection of micronized dHACM at either of the Day 180, Day 270, and Day 365 time points. The investigators and subjects will remain blind to the initial treatment assignment at this time, and until the study is unblinded.

Subjects who receive the open-label access treatment will continue to be followed for 180 days after this second injection, regardless of the time at which treatment was received.

Statistical Methods:

The change in VAS score for pain and Total WOMAC score between baseline and Day 90 (primary endpoints) and between baseline and Day 180 (secondary endpoints) will be compared between the treatment arms using an ANOVA with treatment as a fixed effect and study site as the block effect.

For the purposes of this protocol, we will be examining knee osteoarthritis. The hypothesis to be tested is to confirm that the use of micronized dHACM offers a statistically significant advantage over placebo control.

Efficacy and safety data will be submitted for evaluation following the completion of the study follow-up.

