#### 7.1.3.1 VAS Score for Pain Analysis (90 Days)

[figure not shown]
ANOVA on the change in VAS score for pain between baseline and 90 days with treatment as a fixed effect and study site as the block effect will be used to compare the efficacy between Active and Control groups at 2-sided, level of significance.

In the case of data not being normally distributed, nonparametric tests, such as Wilcoxon Rank Sum test, will be utilized to assess the treatment efficacy.

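### Read in order, the synopsis places the baseline evaluation after the injection, which would make the reference value for both co-primary change scores a post-treatment measurement

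*Protocol*

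**What the plan says.** The Procedures and Assessments part of the protocol synopsis describes a treatment stage of about one day, with these steps: "Screening, pre-procedure evaluation, injection procedure, baseline evaluation". Baseline comes last and is a separate item from the pre-procedure evaluation. The next item says that VAS pain, VAS satisfaction, WOMAC and KOOS "will be evaluated at baseline, 30 days, 60 days, 90 days, 180 days, 270 days and 365 days after the initial treatment", without placing baseline before or after the injection.

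The co-primary endpoints are "The change in VAS score for pain between baseline and Day 90" and "The change in WOMAC osteoarthritis index total score (Total WOMAC score) between baseline and Day 90". The secondary endpoints are the same two changes at 180 days.

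The protocol's Statistical Methods compare all four by ANOVA with treatment as a fixed effect and site as a block. SAP 7.1.3.1 repeats this for the first co-primary: "ANOVA on the change in VAS score for pain between baseline and 90 days". SAP 7.1.6 marks covariate adjustment as not applicable.

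Inclusion criterion 4 reads "Subject must have a VAS pain scale greater than 45". Subjects who meet an exclusion criterion "will be excluded from enrollment and subsequent randomization", so eligibility is settled before allocation.

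**The concern.** A baseline must precede randomisation and treatment if it is to be free of treatment effects. Randomisation balances the arms on what was measured before it, but gives no such protection to a score recorded after the injection. Such a score could carry needle pain, joint distension, an immediate reaction to the material or an immediate placebo response. The arms receive different materials, a micronized tissue product and saline, so equal immediate reactions cannot simply be assumed.

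The reference value of all four confirmatory change scores depends on this point. More acute pain after dHACM would raise its baseline and look like improvement by Day 90. Less acute pain would lower its baseline and hide a real benefit. If some sites measured before the injection and others after, they would not be estimating the same change. The analysis could not repair this later unless a pre-injection score had been kept.

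**Working it through.** **1. What the text fixes.**

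- Order: the first three listed items (screening, pre-procedure evaluation, injection) are in time order. Baseline follows them.
- Separate steps: pre-procedure and baseline evaluation are different items, so the text does not let one stand for the other.
- VAS: the eligibility criterion implies that some VAS precedes randomisation, but the visible text does not call it the baseline.
- WOMAC: no WOMAC before the injection is mentioned in the visible text.
- SAP: sections 2.1, 3.1 and 7.1.3.1 use baseline without a time. Sections 5, 6 and 7.1.2 appear only as headings, so their content is unknown.

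**2. How a post-injection baseline enters the result.** Let Δ be the true Day-90 difference (dHACM minus saline) and δ the between-arm difference in the immediate post-injection score. The unadjusted change-score analysis estimates

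Δ − δ.

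Lower VAS is better. With Δ = 0, a positive δ (more acute pain after dHACM) gives a negative estimate, which looks like benefit. A negative δ does the reverse. If the injection moves both arms equally, δ = 0 and the comparison is unbiased, although the within-arm changes are shifted.

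**3. Inputs for scale.** The plan has no figure on this point to reproduce. Its visible design figures are approximately 466 subjects at 1:1, so 466/2 = 233 per arm. The sample size cannot be re-derived because the effect size, SD, significance level, power and dropout allowance are not visible. The SDs, the 5% level, zero dropout and the shifts below are assumptions.

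**4. False rejection on the VAS test alone, Δ = 0.**

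SE = SD × √(2/233). With SD 25 mm, SE = 25 × 0.09265 = 2.316 mm.

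Rejection probability = P(|Z + δ/SE| > 1.96).

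- δ = 1 mm: 1/2.316 = 0.432, probability 0.07
- δ = 3 mm: 3/2.316 = 1.295, probability 0.25
- δ = 5 mm: 5/2.316 = 2.159, probability 0.58

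Across assumed SDs:

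| SD (mm) | δ = 1 mm | δ = 3 mm | δ = 5 mm |
|---|---|---|---|
| 20 | 8% | 37% | 77% |
| 25 | 7% | 25% | 58% |
| 30 | 7% | 19% | 44% |

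**5. Trial level.** Both co-primaries must succeed, so the trial-level rate cannot exceed the smaller of the two single-test rates. If Total WOMAC had no true effect and no acute shift, its test would reject 5% of the time, and that would cap the joint rate whatever happened to VAS. The cap rises only if WOMAC also shifts.

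**6. The opposite harm, loss of power.** With 233 per arm, the detectable standardised difference is (1.960 + 0.842) × 0.09265 = 0.260 at 80% power, or (1.960 + 1.282) × 0.09265 = 0.300 at 90%. If a post-injection baseline already held a share f of the Day-90 difference, the estimated difference would shrink to (1 − f) of its size:

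| f | power if planned at 80% | power if planned at 90% |
|---|---|---|
| 10% | 71% | 83% |
| 20% | 61% | 74% |
| 30% | 50% | 62% |

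The values of f are assumptions.

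**The case against.** The strongest reply is that this is a comma-separated synopsis list, not a procedure. It has no step numbers or clock times, it omits consent and randomisation, and it does not say that VAS or WOMAC is completed after the needle. Sites would normally work from a visit schedule. SAP section 6 (Study Design and Plan), where one might be found, is visible only as a heading. This stands as a limit: the line does not prove that any score was or will be taken after injection. It does not remove the point. If a definition elsewhere puts baseline first, the synopsis conflicts with it and still needs correcting.

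A second reply is that nothing in the documents indicates an acute difference between the arms, that equal shifts cancel, and that the rejection rates rest on an assumed SD and assumed shifts for one of two required endpoints. This also stands, and so the figures are offered for scale only. Nor can the shift on WOMAC be taken as equal to that on VAS: WOMAC is a 24-item index of pain, stiffness and function, and the visible text gives no basis for equating the two.

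Three stronger readings are tempting but unsupported:

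- A reader might infer that the plan has no definition of baseline. Too much of the SAP is not visible to say so.
- A reader might infer that the VAS that qualifies a subject must also be the baseline value. The listed order does not imply this, and selecting on a score and then using it as baseline invites regression to the mean in within-arm change.
- A reader might infer that the Day-180 score could follow the open-label injection. The treatment-stage line does not concern that visit.

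**Conclusion.** The point holds as a statement about the written order and its consequence. As listed, baseline follows the injection; nothing visible overrides that; and the unadjusted change-score analysis would pass any immediate between-arm difference into the result at full size. This is more than a missing detail, because the stated order would itself produce an endpoint open to bias.

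It is not a finding that the co-primary results are biased. Bias requires both that sites follow the order and that the immediate effect differs between arms. The documents establish neither. Its direction could favour either arm, and its size cannot be derived. With the assumed SD of 25 mm, 233 per arm and two-sided 5%, shifts of 1 to 5 mm would give about 7% to 58% rejection on VAS alone, with a lower trial-level rate under the co-primary rule. The correction is worth making because the reference value of both co-primaries depends on it, and the cost is very small.

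**What to change.** - Protocol synopsis: reorder the treatment-stage line so that the baseline VAS, WOMAC and KOOS evaluation precedes randomisation and injection.
- SAP: state, or confirm if it is already defined, that baseline is the last value recorded before randomisation and injection.
- Visit worksheet: record the time of the baseline assessment.
- If a post-injection score is wanted, hold it as a separate variable that is never used as baseline.
- If subjects have already been treated, adopt the same definition and check recorded assessment times before any unblinding.

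The cost is one reordered line, one SAP sentence and one recorded time. No visits, procedures or subjects are added. For subjects already treated, there is the further work of checking existing records.

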#### **TABLE OF TABLES**

#### **TABLE OF FIGURES**

This Statistical Analysis Plan (SAP) is intended to act as an outline for the statistical interpretation of the data resulting from the Phase 2B Investigational New Drug (IND) trial, titled: "A Phase 2B, Prospective, Double-Blinded, Randomized Controlled Trial of the Micronized dHACM Injection as Compared to Saline Placebo Injection in the Treatment of Osteoarthritis of the Knee." Specific questions regarding this trial's design and/or implementation may be addressed by the study protocol (AIOA001 Protocol V2).

This study consists of two phases – Main Phase and Open-Label Extension Phase (Extension Phase). The Main Phase of the study includes subjects during the observation period where they received the randomized treatment only. The Extension Phase of the study includes the subjects who elected to receive an open-label injection of micronized dHACM injection at either of the 180-day, 270-day or 365-day visits, during the 180-day period following the open-label injection.

In order to facilitate the planning of a Phase 3 pivotal study based on results of the primary and secondary efficacy parameters at 90-day and 180-day, the randomized treatment for the Main Phase will be unblinded and a snapshot of the database will be taken after all randomized subjects completed the 180-day assessment. Formal database preparation process will be performed to ensure the integrity and quality of the database and an interim analysis of the primary and secondary efficacy endpoints as well as the exploratory efficacy endpoints up to the 180-day time point will be performed. At the end of the study, the database will be locked. The database lock process will be performed to ensure the integrity and quality of the database; and formal analyses will be performed.

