#### 4 EXPLORATORY OBJECTIVES

[figure not shown]
The exploratory objectives of this study are intended to assess further the effectiveness in pain reduction and level of disability after being treated with micronized dHACM as compared to the 0.9% sodium chloride, USP placebo control in patients with osteoarthritis of the knee, throughout the course of the study.

As outlined in AIOA001 protocol, all study subjects will become eligible to receive an open-label injection of micronized dHACM at either of the 180-day, 270-day, or 365-day time points. Due to this change in treatment from the original protocol, all endpoints following the 180-day time point become exploratory objectives.

[figure not shown]

Page 6 of 27

[figure not shown]

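### The Day 270 and Day 365 comparison is limited to subjects who have not chosen open-label dHACM, so it is open to selection bias; a model in all randomised subjects would be a cheap improvement

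*Protocol*

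**What the plan says.** The protocol synopsis (Sample Size) gives the size and allocation: "Approximately 466 subjects will be enrolled in this study" and "Subjects to be randomized 1:1 in treatment arms". Under Study Plan, a second injection, of active product, "will be offered to all subjects at the 180-day, 270-day, and 365-day time points". Each subject may use it once, and the initial assignment stays blinded. The SAP introduction describes the Extension Phase as the "subjects who elected to receive an open-label injection of micronized dHACM injection", so uptake is the subject's choice. The visible text sets no response criterion and no expected uptake.

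Under Exploratory Endpoint, the synopsis defines the main-phase cohort as those "who did not receive or have not yet received an open-label injection". VAS pain, Total WOMAC, the WOMAC subscales, VAS satisfaction and KOOS are assessed in that cohort, including at Days 270 and 365. The SAP introduction agrees: "The Main Phase of the study includes subjects during the observation period where they received the randomized treatment only". Scores after the open-label injection go to a separate extension cohort, where they are collected and summarised.

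SAP Section 4 states the exploratory aim as effectiveness against saline over the whole study. It also accepts that, because of open-label access, "all endpoints following the 180-day time point become exploratory objectives".

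**The concern.** Up to Day 180 the arms are comparable because they were randomised. From then on, a subject stays in the main-phase cohort only by not choosing the open-label injection. That choice plausibly depends on current pain, which an effective treatment changes. Blinding does not prevent this, because subjects know their own pain. If dHACM works and poor responders switch, more saline subjects leave and those who stay are the better-off ones. The remaining saline group then looks too good, and the difference shrinks.

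At stake is the only randomised evidence on whether one injection lasts beyond 180 days. Labelling the endpoints exploratory limits the claims made from them but does not make the cohort comparable.

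**Working it through.** **Plan's own figure.** 466 randomised 1:1 is 233 per arm. The visible text does not give the effect size, SD, power, dropout and significance level needed to re-derive it, so it is used only as a starting count.

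**1. Visits affected.** Assume that scores at a visit are taken before that visit's injection (the order is not stated). Days 30 to 180 then lose nobody to open-label access. Day 270 loses the Day 180 switchers, and Day 365 loses the Day 180 and Day 270 switchers.

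**2. Loss of subjects.** Remaining = 466 × (1 − u), where u is cumulative uptake. Illustrative power uses m = 233 × (1 − u) per arm, an assumed effect of 0.30 SD and an assumed two-sided 0.05 level: power = Φ(0.30 × √(m/2) − 1.96).

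| u | Remaining | Power |
|---|---|---|
| 0 | 466 | 90% |
| 20% | 373 | 83% |
| 30% | 326 | 77% |
| 50% | 233 | 63% |

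**3. Direction of bias, in SD units.** Take improvement at Day 180 as normal with SD 1 and mean 0 (saline) or 0.30 (active), the same true effect at Day 270, and correlation ρ between the visits. Everyone below a common threshold t switches. The retained-group estimate is 0.30 + ρ × (λ_active − λ_saline), where λ = φ(t − μ) / [1 − Φ(t − μ)] and μ is the arm mean.

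At 50% overall uptake, t = 0.15:
- Saline: λ = 0.3945 / 0.4404 = 0.896 (56% switch).
- Active: λ = 0.3945 / 0.5596 = 0.705 (44% switch).
- Estimate: 0.30 − 0.191ρ, which is 0.20 at ρ = 0.5 and 0.17 at ρ = 0.7.

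Simulation with 2,000,000 per arm agrees and covers other rules:
- Worst responders switch: 0.22 to 0.24 at 20% uptake, 0.17 to 0.20 at 50%.
- Response only partly drives switching: 0.26 to 0.27 at 20%, 0.23 to 0.25 at 50%.
- Switching unrelated to response: 0.30, no bias.
- True effect zero throughout, same rule in both arms: 0, no bias.
- Best responders switch, same rule: 0.17 to 0.21 at 50%.
- Extreme arm-specific rule (worst active and best saline responders leave, 30% each): 0.80 to 0.99, so the direction reverses.

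**4. Size on the VAS.** All inputs are assumed: follow-up SD 25 mm; correlation 0.7 between follow-up visits and 0.3 with baseline; baseline mean 60, SD 20, truncated at the entry limit of 45; uptake 40% at Day 180 and 24% of the remainder at Day 270. Logistic uptake slopes of 0.5, 1.0 and 1.5 per SD of pain correspond to odds ratios of 1.6, 2.7 and 4.5.

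| True lasting effect | Day 270 | Day 365 |
|---|---|---|
| 6 mm | 5.9, 5.5, 5.3 | 5.8, 5.0, 4.9 |
| 10 mm | 9.8, 9.2, 8.6 | 9.5, 8.5, 7.9 |

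Simulation error is about 0.1 mm: 600,000 subjects with 60% retained is 180,000 per arm, and 25 × √(2/180,000) = 0.08. Varying the baseline mean between 60 and 65 widens the 6 mm row to about 5.1–5.9 at Day 270 and 4.6–5.8 at Day 365. The attenuation is (6 − 5.9)/6 = 2% to (6 − 5.1)/6 = 15% at Day 270, and (6 − 5.8)/6 = 3% to (6 − 4.6)/6 = 23% at Day 365.

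If an 8 mm effect at Day 180 has gone by Day 270, the retained cohort favours saline by about 0.2 to 1.2 mm at Day 270.

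**5. Against sampling error.** With these inputs the standard error of the arm difference is about 2.9 to 3.4 mm. The largest bias for a 6 mm effect is 6 − 4.6 = 1.4 mm, and 1.4/2.9 = 0.48, so it stays below half a standard error.

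**6. Does a model help?** Adding baseline as a covariate within the restricted cohort does not cure the attenuation (5.1 to 5.9 mm at Day 270). A likelihood model in all randomised subjects, using every pre-injection score, returned 5.8 to 6.1 mm and 9.9 to 10.1 mm for true effects of 6 and 10 mm. Uptake was generated from recorded scores, so this recovery is expected by construction. It does not test switching for unrecorded reasons.

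**The case against.** The strongest reply is that the documents already deal with this. SAP Section 4 downgrades everything after Day 180 because of open-label access, and no primary or secondary endpoint depends on the restricted cohort. The text of SAP 7.1.2 (Analysis Set) and 7.1.5 (Exploratory Analyses) cannot be seen, so an all-randomised model or a rule for switchers may already be there. The synopsis says only that these endpoints will be assessed; the between-arm aim comes from SAP Section 4. The likely bias is also small beside the sampling error.

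All of that stands, and it limits the importance of the point. It does not make the stated cohort comparable by randomisation.

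Three stronger readings are tempting and are not supported:
- A reader might infer that the durability estimate is certainly biased. Bias needs uptake related to outcome, and its direction depends on whether both arms follow the same rule.
- A reader might infer that about half the subjects are lost. No uptake rate is stated. Even the assumed 40% and 24% lose 40% at Day 270, and 1 − 0.60 × 0.76 = 54% only at Day 365.
- A reader might infer that Phase 3 planning is compromised. The SAP introduction ties that planning to the Day 90 and Day 180 results, and its planning analysis stops at Day 180.

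**Conclusion.** The point holds in conditional form. The Day 270 and Day 365 cohort is selected by a choice made after randomisation, so a comparison of arms within it is open to selection bias. Under a common, pain-driven uptake rule and the assumed inputs, a lasting 6 mm effect is understated by roughly 0.1 to 0.9 mm at Day 270 and 0.2 to 1.4 mm at Day 365. Precision falls in proportion to uptake, which is unknown. The Day 90 endpoints are untouched, and so are the Day 180 endpoints if scored before the injection. This is a worthwhile, inexpensive improvement to an exploratory analysis and not a flaw in the trial's main conclusions.

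**What to change.** Unless SAP 7.1.2 or 7.1.5 already provides this:

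- For Days 270 and 365, estimate the arm difference in all randomised subjects with a repeated-measures model containing treatment, visit, treatment-by-visit, site and baseline score. Use every score up to and including the visit at which open-label dHACM is given. Treat later scores as missing, and state that the LOCF rule in SAP 7.1.13 does not apply to them; the visible text does not say how it treats switchers.
- Report open-label uptake by arm and visit.
- Keep the table of subjects not yet injected, as description only.
- Optionally, add an as-randomised analysis of all scores. The scheduled post-injection visits allow it: 180 + 90 = Day 270, 180 + 180 = Day 360 and 270 + 90 = Day 360. Label it as a different estimand, because saline switchers have by then received dHACM.
- Add a sensitivity analysis for the missing-at-random assumption.

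The cost is SAP wording and some extra modelling on data already scheduled. It needs no new visits or subjects, and the primary and secondary analyses do not change. The downside is that the model assumes uptake depends only on recorded scores. That is still weaker than the restricted cohort's implicit assumption that non-switchers are a random subset.
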